### 2.2.3 Phase II Part 2 Primary Objective and Endpoints

To determine whether hydroxychloroquine added to low dose palbociclib and letrozole can increase the proportion of patients whose tumors achieve complete cell cycle arrest (CCCA, defined as the Ki67  $\leq$  2.7%) comparing T2 to T1 as shown in Figure 2, see Section 5.3.4).

The primary endpoint is the increase in percentage of all patients who achieve CCCA with low dose palbociclib and letrozole (at week 2, time T1) compared to that of low dose palbociclib and letrozole with the addition of HCQ (at 5 weeks, day 29, time T2).

A previously conducted trial of neoadjuvant aromatase inhibitor (anastrozole) plus standard dose palbociclib estimated the CCCA probability to be 44% with aromatase inhibitor alone and powered their study to detect a 50% increase of 44% to 66%. A 26% CCCA probability was seen with anastrozole alone and 86% with the addition of standard dose palbociclib. We will aim for a CCCA reference probability of 50% with low-dose palbociclib + letrozole (T1) and a CCCA probability of 75% with the addition of HCQ (see Section 8 for statistical plan and samples size calculations for the Phase II portion).

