### **Phase II:**

The Phase II portion will be performed in a different population of patients (early stage) in the pre-operative setting. In order to obtain qualitative information about the dose responsiveness of HCQ when added to letrozole and palbociclib, Part 1 of the Phase II portion will enroll 6 patients at an HCQ dose of 400 mg (if in fact, the RP2D is 600 or 800 mg). Following this, Part 2 will be conducted at the RP2D for HCQ based on the primary endpoint of proportion of patients achieving tumoral CCCA, with the formal statistical plan using a 2-stage Simon optimal design and looking to increase the CCCA rate from 50% with low dose palbociclib + letrozole to 75% after the addition of HCQ. This design requires 11 patients in the first stage and 14 patients in the 2nd stage. It would stop after the 1st stage if no more than 6 patients show CCCA by tumor biopsy after HCQ treatment and declared the treatment as promising if at least 17 out of 25 total evaluable patients exhibit CCCA.

This design has alpha = 4%, 81% power, and a probability of 0.73 of terminating after the 1st stage if the true CCCA rate=50%. For the group of patients at the RP2D, we therefore plan a sample size of 30 patients over 12-15 months, accounting for patient dropout (including those with Ki67 >10% at T1). We have a large eligible patient population and have led national accruals in other multi-center neoadjuvant endocrine trials in post-menopausal women (e.g. ALTERNATE Trial). In addition, recent local experience of conducting window of opportunity trials in this setting have demonstrated the feasibility of accrual at a rate of ~2 patients per month. Thus, we expect to achieve accrual goals.

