#### ----- DOSAGE AND ADMINISTRATION -----

IBRANCE capsules are taken orally with food in combination with an aromatase inhibitor or fulvestrant. (2)

- Recommended starting dose: 125 mg once daily taken with food for 21 days followed by 7 days off treatment. (2.1)
- Dosing interruption and/or dose reductions are recommended based on individual safety and tolerability. (2.2)

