### **14. Absorption**

The mean maximum observed concentration (Cmax) of palbociclib is generally observed between 6 to 12 hours (time to reach maximum concentration, Tmax) following oral administration. The mean absolute bioavailability of IBRANCE after an oral 125 mg dose is 46%. In the dosing range of 25 mg to 225 mg, the AUC and Cmax increased proportionally with dose in general. Steady state was achieved within 8 days following repeated once daily dosing. With repeated once daily administration, palbociclib accumulated with a median accumulation ratio of 2.4 (range 1.5 to 4.2).

Food effect: Palbociclib absorption and exposure were very low in approximately 13% of the population under the fasted condition. Food intake increased the palbociclib exposure in this small subset of the

population, but did not alter palbociclib exposure in the rest of the population to a clinically relevant extent. Therefore, food intake reduced the intersubject variability of palbociclib exposure, which supports administration of IBRANCE with food. Compared to IBRANCE given under overnight fasted conditions, the population average area under the concentration-time curve from zero to infinity (AUCINF) and Cmax of palbociclib increased by 21% and 38%, respectively, when given with high-fat, high-calorie food (approximately 800 to 1000 calories with 150, 250, and 500 to 600 calories from protein, carbohydrate, and fat, respectively), by 12% and 27%, respectively, when given with low-fat, low-calorie food (approximately 400 to 500 calories with 120, 250, and 28 to 35 calories from protein, carbohydrate, and fat, respectively), and by 13% and 24%, respectively, when moderate-fat, standard calorie food (approximately 500 to 700 calories with 75 to 105, 250 to 350 and 175 to 245 calories from protein, carbohydrate, and fat, respectively) was given 1 hour before and 2 hours after IBRANCE dosing.

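### The Part 2 decision rule tests post-HCQ CCCA against an unsupported fixed 50% and ignores the mandatory T1 reading, so passing it does not show that HCQ increased CCCA

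*Combined protocol and SAP*

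**What the plan says.** Section 2.2.3 describes the Part 2 primary endpoint as a change: the rise in the percentage of patients with CCCA (Ki67 at or below 2.7%) between T1, after two weeks of low-dose palbociclib plus letrozole, and T2, after HCQ has been added. Sections 3.1 and 3.4 describe it the same way.

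The planning rates are introduced as an aim: "We will aim for a CCCA reference probability of 50% with low-dose palbociclib + letrozole (T1) and a CCCA probability of 75" per cent with HCQ. The background figures just before this are a prior trial's planning values (44% and 66%) and its observed results: "A 26% CCCA probability was seen with anastrozole alone and 86% with the addition of standard dose palbociclib".

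Section 8.0 then sets a Simon optimal two-stage design, "looking to increase the CCCA rate from 50% with low dose palbociclib + letrozole to 75% after the addition of HCQ". Eleven patients enter stage 1 and 14 enter stage 2. The trial stops if 6 or fewer of the first 11 have CCCA after HCQ, and it "declared the treatment as promising if at least 17 out of 25 total evaluable patients exhibit CCCA". The stated properties are alpha 4%, power 81% and a 0.73 probability of early termination at a true rate of 50%.

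Three other provisions matter. Section 3.6 requires interpretable Ki67 at T0, T1 and T2 for evaluability. Section 5.2.3.2 takes patients with T1 Ki67 above 10% off study, and Section 8.0 counts them as dropout. Section 3.7 replaces patients who are not evaluable.

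**The concern.** The endpoint is a within-patient change, but the rule is a one-sample test of the T2 proportion. The T1 result is obtained for every evaluable patient and does not enter the rule. The doublet's contribution is represented only by the assumed 50%, for which no source or derivation is given. The documents contain no CCCA rate for 75 mg continuous palbociclib with letrozole.

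If the doublet alone gives more than 50% among evaluable patients, the rule credits that excess to HCQ, and the stage 1 stop loses much of its protection. The T1 removal rule pushes in the same direction: it takes out only patients who are not in CCCA and refills their places. At stake is a favourable conclusion about HCQ that the data behind it may not support.

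**Working it through.** **Inputs.** From Section 8.0: n1 = 11, stop if 6 or fewer; n2 = 14, total 25; promising if 17 or more. Planning rates 50% and 75% (Sections 2.2.3 and 8.0). T1 removal at Ki67 above 10% (Section 5.2.3.2). Thirty enrolled for 25 needed (Section 3.8).

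**Formulas.** With p the true CCCA rate among evaluable patients at T2:

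- early stop = P(Bin(11, p) ≤ 6)
- promising = Σ over x = 7 to 11 of P(Bin(11, p) = x) × P(Bin(14, p) ≥ 17 − x)

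**Reproducing the plan's figures.** At p = 0.50 the five terms (x = 7 to 11) are 0.0145 + 0.0171 + 0.0106 + 0.0033 + 0.0004, which sum to 0.0458 before rounding of the terms. Early stop is 0.7256. At p = 0.75 the probability of promising is 0.8005. A search for the Simon optimal design with alpha at most 5% and power at least 80% returns exactly 6/11 and 17/25. The design, the early-stop probability (0.73) and, to within a point, the power (80% against 81%) are confirmed. Alpha is 4.6%, not 4%.

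**If HCQ adds nothing**, p is the doublet's own rate among evaluable patients:

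| Doublet rate | Declared promising | Stops after stage 1 |
|---|---|---|
| 40% | 0.4% | 90% |
| 50% | 4.6% | 73% |
| 55% | 11.5% | 60% |
| 60% | 24.0% | 47% |
| 65% | 41.7% | 33% |
| 70% | 62.0% | 21% |
| 75% | 80.1% | 11% |

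The false-positive probability passes 10% at a doublet rate of 54.1% and 20% at 58.6%.

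**Effect of the T1 removal rule.** A patient with Ki67 above 10% is by definition not in CCCA. If 50% holds for all patients biopsied at T1 and a fraction f is removed and replaced, the rate among those remaining is 0.50 / (1 − f). The documents do not give f, so these are assumed values:

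- f = 10%: 0.50 / 0.90 = 55.6%; false positive 12.6%
- f = 5/30 = 16.7% (all five allowed dropouts): 0.50 / 0.833 = 60%; false positive 24.0%
- f = 20%: 0.50 / 0.80 = 62.5%; false positive 32.3%

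**Adding a paired condition (simulated).** Suppose promising also required more conversions to CCCA than losses, by a one-sided exact test on discordant pairs at p ≤ 0.10. Power for 50% to 75% is then 74%, 69% and 64% when 0%, 4% and 10% of patients in CCCA at T1 lose it by T2. With no HCQ effect but a drift from 50% to 60% over the two extra weeks of doublet, the combined rule still passes about 9% of the time.

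**The case against.** The best defence is that 50% is reasonable. It lies between the two observed rates (26% and 86%; midpoint 56%), and the preclinical rationale in Section 1.2, where low palbociclib concentrations give a reversible arrest, argues for a weaker doublet. At 50% or below, the error is at most 4.6% (1.5% at 45%). A fixed historical rate is also usual in a single-arm phase II trial, and this trial will observe T1 anyway.

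Much of this stands. The inflated error is conditional on a doublet rate above 50%, and nothing in the documents shows that it is. But a bracket from 26% to 86% does not justify one value when the result is this sensitive: even the midpoint gives 13.6%. That T1 is observed makes its absence from the rule harder to defend.

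A reader might go further in three ways that the documents do not support.

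- **Taking 86% as the real null.** That figure belongs to standard-dose palbociclib with anastrozole. It does not estimate the low-dose rate.
- **Scaling by dose.** The label gives "Recommended starting dose: 125 mg once daily taken with food for 21 days followed by 7 days off treatment", so 75 mg continuous is 80% of the 28-day total, and scaling the 26% to 86% increment by 80% gives about 74% for the doublet. But T1 follows 14 days of continuous dosing, which a 28-day total that includes the off-week does not describe. Dose-proportional exposure ("In the dosing range of 25 mg to 225 mg, the AUC and Cmax increased proportionally with dose in general") says nothing about how often Ki67 falls to 2.7% or below.
- **Arguing that 17/25 falls short of 86%.** The exact 95% interval for 17/25 ends at 85.1%, but for 18/25 it ends at 87.9%. The 86% is cited without a sample size, and the plan makes no claim of parity with standard dose.

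**Conclusion.** The concern holds in conditional form. The 50% reference is unsupported, the rule ignores the T1 data that the endpoint is defined on, and the stated error rate describes one assumed doublet rate. With no HCQ effect, the chance of a promising verdict is 4.6% at a doublet rate of 50%, less below that, 24% at 60%, 62% at 70% and 80% at 75%. The T1 removal rule can move the evaluable-set rate to between 55.6% and 60% even if 50% is right overall, assuming 10% to 16.7% are removed.

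The documents do not show that a false positive is likely, because the low-dose rate is unknown. They do show that meeting 17/25 establishes only that T2 CCCA exceeds 50% among evaluable patients. The calculations treat patients as independent with a common rate. The no-effect scenarios also assume no change from two further weeks of the doublet.

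**What to change.** 1. **Section 8.0, wording.** Correct alpha to 4.6% and power to 80%. Tabulate the pass and early-stop probabilities for doublet rates from 50% to 75%. State that 17/25 shows only that T2 CCCA exceeds 50% among evaluable patients and is not by itself evidence of an HCQ effect.
2. **Paired analysis.** Keep 6/11 and 17/25 as the activity screen. Prespecify the T1-to-T2 comparison in the same patients: conversions to CCCA against losses, an exact test on discordant pairs, and the difference with its confidence interval. Any statement that HCQ increased CCCA must rest on this analysis.
3. **Reporting.** Give T1 CCCA among all patients biopsied at T1, including those removed for Ki67 above 10%, so that the doublet rate and the effect of removal can be seen.

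**Cost.** No added patients or biopsies. The stated error becomes less favourable. If the sponsor makes the paired test a formal condition at one-sided p ≤ 0.10, power for 50% to 75% falls from 80% to about 64–74%; that is a choice, not a necessity. Without a concurrent control, the paired comparison cannot separate HCQ from two more weeks of the doublet, and the protocol should state this as a limitation.

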### 2.2.4 Phase II Part 2 Secondary Objectives and Endpoints

- To determine the impact of adding hydroxychloroquine to low dose palbociclib and letrozole on breast tumor indices of proliferation, autophagy, senescence, cell cycle control and other intersecting pathways.
- Determine longer term clinical tumor responsiveness and tumor biomarkers indices (for patients who have extended pre-operative therapy, maximum 24 weeks).
- To determine the dose responsiveness of HCQ (400 mg vs. RP2D) on the primary (proportion with CCCA) and secondary clinical/biological endpoints
- To perform exploratory studies on blood-based tumor protein, DNA and RNA biomarkers.
- Obtain additional safety information for the combination of low dose palbociclib, letrozole and hydroxychloroquine.

## 3.0 INVESTIGATIONAL PLAN

### 3.1 Overall Design

This is an open label Phase I/II prospective interventional trial with a safety component in metastatic disease followed by a “window” trial component in the neo-adjuvant (pre-operative) setting.

#### Phase I Safety Component:

The Phase I is designed to evaluate the safety and tolerability of adding HCQ to continuous low dose palbociclib and letrozole in the metastatic setting and to determine the recommended phase 2 dose for HCQ. A standard 3+3 dose escalation designed will be employed.

This safety component will be completed before the initiation of the window trial (Phase II) in the pre-operative setting.

[figure not shown]
#### Phase II Pre-operative “Window” Component:

The “window” component of the trial evaluates the combination of pre-operative palbociclib plus letrozole followed by the addition of hydroxychloroquine (HCQ) for postmenopausal patients with Stage I-III estrogen receptor-positive and HER2-negative breast cancer (Figure 2).

Correlative studies using baseline and follow up breast biopsies and blood work are included in the research plan. The Phase II portion will assess the change in the percentage of all patients who achieve CCCA when adding HCQ to the palbociclib/letrozole combination.

## 3.2 TRIAL SCHEMATA

### 3.2.1 Trial Overview Schema Design and Flow

[figure not shown]

**Figure 1: General schema for both phases of the trial.** The run-in Phase I safety study done in the metastatic setting will establish safety and determine the Phase II dose. The Phase II study will assess two doses of HCQ (400 mg in 6 patients and RP2D in 30 patients) added to continuous low dose palbociclib plus letrozole and assess proliferative index (Ki67) pre and post HCQ administration.

### 3.2.2 Window Component Schema and Design

## Phase II Window Component Trial Schema

- Post menopausal
- Clinical Stage I-III Breast Cancer
- ER+, HER2-negative
- No Prior Therapy

**FIGURE 2. Schema for pre-operative “window”/neoadjuvant trial.** Part 1 dose responsiveness evaluation at 400 mg/d HCQ followed by Part 2 at RP2D HCQ using same design and biopsy time points (T0 [baseline/pretreatment, T1 [after 2 weeks P+L], T2 [after addition of HCQ]), with option to proceed with surgery right after T2 biopsy or up to 24 weeks from initiation of therapy. P=continuous low dose palbociclib at 75 mg daily L=letrozole at 2.5 mg daily; HCQ=hydroxychloroquine continuous daily at assigned dose; N=number of patients; U/S=ultrasound; RP2D=recommended Phase II dose (of HCQ).

## **Design for the Safety Component/Phase I**

A cycle will be defined as 28 days, with dose limiting toxicity (DLT) assessed over the first cycle.

The dose of letrozole and palbociclib will be fixed for the safety cohorts at:

- **Palbociclib:** 75 mg capsule taken orally once daily on a continuous basis.
- **Letrozole:** 2.5mg/d taken orally once daily continuously.

### Hydroxychloroquine Dose Escalation Scheme

Dose Level (DL)	Hydroxychloroquine	Letrozole	Palbociclib
0 (Starting Dose)	400 mg/d	2.5 mg daily	75 mg daily (continuous)
+1	600 mg/d		
+2	800 mg/d		

The dose escalation portion will use a 3+3 dose escalation design to evaluate escalating dose levels of HCQ in combination with palbociclib and letrozole (see dose level table above). Three patients will be enrolled at the first dose level (DL 0, 400 mg daily) of the triplet combination. At least 3 patients must complete a treatment cycle (28 days) with the triple combination and undergo toxicity assessment before any additional patients are enrolled into higher dosing cohorts. Intrapatient dose escalation or change of dosing schedule is not allowed. At least 6 evaluable patients are to be treated at a dose level for a RP2D to be declared.

- If 0 out of 3 patients in a dose level experience a DLT in the defined timeframe another 3 patients will be enrolled at the next higher dose level.
- If no more than 1 patient experienced a DLT at a dose level, then more patients will be added to that cohort to increase the cohort up to six patients at the same dose level
- If no more than one of the first 6 patients treated experiences a DLT, then 3 patients will be enrolled at the next higher dose level.
- If two or more of the first 6 patients treated within a cohort experience DLT, then this dose level will be considered not tolerated and the dose escalation will be halted. If two DLTs are seen in any cohort, no further patients will be enrolled at that level and next level lower will be declared the RP2D.

The RP2D is defined as the highest dose level at which 6 patients have been treated with at most 1 instance of DLT.

If two DLTs are seen at the starting dose of 400 mg (DL 0), then this treatment will be declared to not be feasible as doses of HCQ < 400 mg may be too low for the intended effects.

The Principal Investigator will monitor safety throughout the study, review patient data and make decisions prior to advancing to the next dose level, approve dose escalation, and will also declare the establishment for RP2D and declare when the Phase II part of the study can commence.

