### **3.8 Target Accrual**

A total of 54 patients will be enrolled to the study. This includes 2 to 18 patients (up to 6 per dose cohort at 400, 600 and 800 mg of HCQ daily and 6 at the RP2D, but as few as 2 patients in the unlikely event that the first 2 patients experience DLT at the lowest dose of HCQ (400 mg daily) and the study is halted.) in the Phase I metastatic portion, 6 patients for neo-adjuvant Phase II Part 1 and 30 patients for the Phase II Part 2 portion (25 needed for statistical plan and 5 expected to drop out). This does not account for replaced patients (as stated in Sections 3.6 and 3.7).

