## **8.0 STATISTICAL CONSIDERATIONS**

### **Phase I:**

For the phase I portion, a 3+3 design will be used with 3 to 6 patients for each dose escalation cohort (depending on whether a DLT is seen) and 6 patients in the final (RP2D) cohort to assess the primary endpoint of safety and the determination of RP2D. Therefore a minimum of 12 and maximum of 18 patients will be enrolled. This total does not include patients who may need to be replaced if not evaluable for DLT (see Section 3.3).

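### Phase I has no single rule for declaring the RP2D: after two DLTs one bullet names the next lower level with no patient count, four other statements require six patients, and the stated minimum of 12 and the DLT list also need reconciling

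*Combined protocol and SAP*

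**What the plan says.** **Declaring the RP2D.** Under the Hydroxychloroquine Dose Escalation Scheme, 0 DLTs in 3 patients leads to enrolment at the next level. The next bullet reads "If no more than 1 patient experienced a DLT at a dose level, then more patients will be added to that cohort", up to six. The fourth bullet says that once two DLTs occur in any cohort, "no further patients will be enrolled at that level and next level lower will be declared the RP2D". The paragraph before the bullets says "At least 6 evaluable patients are to be treated at a dose level for a RP2D to be declared". The sentence after them says "The RP2D is defined as the highest dose level at which 6 patients have been treated with at most 1 instance of DLT". Section 3.8 plans "up to 6 per dose cohort at 400, 600 and 800 mg of HCQ daily and 6 at the RP2D", and Section 8 (Phase I) plans "6 patients in the final (RP2D) cohort to assess the primary endpoint of safety".

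**Phase I size.** Section 8 concludes: "Therefore a minimum of 12 and maximum of 18 patients will be enrolled". Section 3.8 gives 2 to 18, with "as few as 2 patients in the unlikely event that the first 2 patients experience DLT at the lowest dose of HCQ".

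**DLTs.** Section 3.3 lists every non-hematologic toxicity of Grade 3 or above, with no duration. It also lists Grade 3 or higher nausea/vomiting or diarrhea (at least 72 hours), fatigue (at least 1 week) and electrolyte abnormality (more than 72 hours, or any duration if symptomatic). For neutropenia it lists neutropenic fever and Grade 4 lasting more than 7 days. Section 6.2.3 adds any Grade 3 toxicity attributed to HCQ in the first 28 days.

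**The concern.** A level passed on 0/3 holds three patients. If the level above fails, the fourth bullet makes that three-patient level the RP2D, while four other statements say it cannot yet be one. The step that would join them, returning to the lower level and treating three more, is not written. The first two bullets also overlap: no more than one DLT includes none, so 0/3 carries two instructions, escalate and expand.

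The RP2D goes to 30 early-stage patients in Phase II Part 2 and is the dose of the primary efficacy test. Section 1.3 justifies entering a curable population only after safety has been established in advanced disease. The number of patients behind that judgement should not depend on which sentence is followed.

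The DLT list feeds the same decision. With a two-DLT stopping rule, reclassifying one event can change the dose.

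**Working it through.** **Enrolment range.** The maximum reproduces: 3 levels × 6 = 18, and 18 + 6 + 30 = 54, the Section 3.8 total. The figure 12 is 3 + 3 + 6: 0/3 at 400 mg, 0/3 at 600 mg, then six at 800 mg. It is not the design's minimum:

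| Outcome | Stop at second DLT | Full cohorts of 3 |
|---|---|---|
| Not feasible at 400 mg | 2 | 3 |
| RP2D declared, literal bullet | 3 + 2 = 5 | 3 + 3 = 6 |
| RP2D declared, six-patient rule | 6 + 2 = 8 | 6 + 3 = 9 |

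If the second bullet were applied at 0/3 on every level, an RP2D of 800 mg would need 6 + 6 + 6 = 18, so 12 depends on the first bullet prevailing.

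**How often the two rules differ.** The documents give no DLT rates, so the rates below are assumptions. For a level with DLT rate p:

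- a = (1−p)³, the chance of 0/3;
- b = 3p(1−p)² × (1−p)³, the chance of 1/3 followed by 0/3;
- s = 1 − a − b, the chance the level fails;
- f = 3p²(1−p) + p³, the chance of two or more DLTs in three patients.

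At 800 mg, 0/3 is expanded to six, so s₃ = 1 − [(1−p)⁶ + 6p(1−p)⁵].

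P(RP2D rests on 3) = a₁s₂ + (a₁+b₁)a₂s₃.

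P(expanding to six overturns it) = a₁s₂f₁ + (a₁+b₁)a₂s₃f₂.

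Worked for 10/20/30% at 400/600/800 mg: a₁ = 0.7290, b₁ = 0.1771, a₂ = 0.5120, s₂ = 0.2914, s₃ = 0.5798, f₁ = 0.028, f₂ = 0.104.

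- Rests on 3: 0.7290 × 0.2914 + 0.9061 × 0.5120 × 0.5798 = 0.2124 + 0.2690 = 0.481.
- Overturned: 0.2124 × 0.028 + 0.2690 × 0.104 = 0.0059 + 0.0280 = 0.0339, which is 7.0% of the 0.481.

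Fewer than 12 enrolled, full cohorts:

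- Literal bullet: s₁ + a₁s₂ + b₁f₂ + a₁a₂f₃ = 0.0939 + 0.2124 + 0.0184 + 0.0806 = 0.405.
- Six-patient rule: s₁ + (a₁+b₁)f₂ = 0.0939 + 0.0942 = 0.188.

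| Assumed rates, 400/600/800 mg | 5/10/20% | 10/20/30% | 10/25/40% | 20/35/50% |
|---|---|---|---|---|
| RP2D rests on 3 (bullet) | 32.5% | 48.1% | 58.5% | 48.2% |
| Overturned at six, all trials | 0.7% | 3.4% | 5.4% | 8.1% |
| Overturned, of those resting on 3 | 2.3% | 7.0% | 9.2% | 16.8% |
| Fewer than 12, bullet | 18% | 41% | 52% | 73% |
| Fewer than 12, six-patient rule | 5% | 19% | 24% | 49% |

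Stopping at the second DLT raises the last two rows to 29/55/68/85% and 13/36/47/72%.

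**Information at the RP2D.** One-sided 95% Clopper-Pearson upper bounds on the DLT rate: 0/3, 1 − 0.05^(1/3) = 63%; 0/6, 1 − 0.05^(1/6) = 39%; 1/6, 58%.

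**DLT items side by side.** An asymptomatic Grade 3 electrolyte abnormality of 72 hours or less is a DLT under the blanket item. The electrolyte item's duration limit, and its exception for symptomatic patients, make sense only if it is not. The gastrointestinal and fatigue durations have no effect beside the blanket item. Grade 3 neutropenia without fever is not listed in 3.3 but is a DLT under 6.2.3 if attributed to HCQ. Such events are plausible: Section 1.1.3 cites 66% Grade 3 and 4 neutropenia with palbociclib (standard dose, not this regimen), and the HCQ label in Appendix B lists blood dyscrasias. Attribution alone would then decide DLT status.

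**The case against.** The strongest reply is that the scheme does contain a rule: a six-patient precondition before the bullets and a formal definition after them, echoed in Sections 3.8 and 8. On that view the bullet only lacks its follow-up step, and an RP2D on three patients would breach the definition. This is a fair reading, and the lower level can be taken as a candidate until six are treated. But the bullet says the level will be declared, and the reader has to supply the missing step.

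The second bullet might itself be that step if it covers 0/3. It then competes with the first bullet, and nothing says it applies after a higher level has failed.

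On DLTs, the list is of alternatives, so the gastrointestinal and fatigue items are redundant rather than contradictory. Section 7.1 treats laboratory abnormalities as adverse events only if symptomatic, clinically significant or needing therapy, which narrows the electrolyte example. The wording of 6.2.3 is additive, yet Section 2.1.1 sends the reader to 3.3 for the DLT definition. Those points soften this part; the mismatch between 3.3 and 6.2.3 remains.

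On size, the percentages rest on assumed rates. At 5/5/10% the RP2D rests on three patients in 12% of trials and is overturned in 0.1%. No decision rule uses the figure 12. Investigator review and IND Office approval at dose changes (Section 8.1) are real safeguards, but neither says which rule applies.

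**Conclusion.** The concern holds. The text supports two incompatible conditions for declaring the RP2D, and they diverge whenever the lower level was passed on 0/3 and the level above fails. Under the four assumed profiles the literal bullet takes that three-patient path in about a third to over half of trials. The dose itself would change in 0.7% to 8.1%, a minority. The gain in information is clear if the enlarged level ends at 0/6 (bound 39% against 63%) and small if it ends at 1/6 (58%). If the lower level was already expanded after 1/3, the two rules agree.

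The Section 8 minimum of 12 is wrong as a minimum under either rule; this needs no assumed rates. The DLT inconsistency is textual, and its effect on dose selection cannot be sized from the documents. Overall this is a point that should be corrected before dose decisions are made.

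**What to change.** 1. Reconcile the fourth bullet, and the overlapping first and second bullets, with the six-patient statements so that one rule governs RP2D declaration. State what happens when a level passed on 0/3 lies below a level that fails.
2. Restate the Section 8 range to agree with Section 3.8, and label 12 as the path without DLTs if the first bullet is kept.
3. Reconcile the blanket Grade 3 item, the duration-limited items and Section 6.2.3 so that each event has one DLT status.

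Which clinical rule applies is for the sponsor to decide. Items 1 and 2 are wording changes, and the maximum of 18 already allows six patients at each of the three levels. Item 3 is also a text change, but if it alters which events count as DLTs it is a substantive safety amendment and should be handled as one.
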